2.1.1.5 Study day

The study day for a baseline or post-baseline scheduled or unscheduled visit is defined as:

• Study day = (Date of visit) - (Baseline date) + 1

For visits prior to baseline, the study day is defined as:

• Study day = (Date of visit) - (Baseline date)

2.1.1.6 Baseline date

Baseline date is referred to as Day 1 of the study. It is defined as the date of first administration of study treatment in this study for treated patients. If a patient is randomized but not treated then the baseline date is defined as the date of randomization.

2.1.1.7 Baseline and post-baseline definitions

The baseline value for efficacy and safety variables is the last available, non-missing, (scheduled or unscheduled) value collected prior to first administration of study treatment.

Some baseline assessments may be recorded on the day of the Baseline visit (Visit 3/Week 0). However the time of each of these assessments may not be recorded in the eCRF. In this case, only the assessments which, according to the protocol, should have been conducted pre-dose on Day 1 will be assumed to have been done prior to administration of study treatment on Day 1 when deriving baseline values recorded on the day of the Baseline visit (Visit 3/Week 0).

All data collected after the Baseline date are defined as post-baseline.

2.1.1.8 Coefficient of variation

The coefficient of variation (CV) will be calculated as:

• (SD/mean)*100

2.1.1.9 Geometric coefficient of variation

The geometric CV will be calculated as:

• sqrt(exp(variance of log-transformed data)-1)*100

2.1.1.10 Geometric mean

The geometric mean will be calculated as:

• exp((sum of log transformed data) / number of non-missing data points after log transformation)

2.1.1.11 Change from baseline and relative change from baseline definitions

Change from baseline and relative change from baseline will only be summarized for patients with both baseline and post-baseline data for the relevant visit and will be calculated using the following formulae:

- Change from baseline = Post-baseline value baseline value
- Relative change from baseline (%) = 100 × ([Post-baseline value baseline value] / baseline value)

2.1.1.12 Visit windowing

The study day for each visit will be derived; this day will then be used to determine the analysis visit based on the visit windows outlined in Table 2-1. In addition the study day associated with each week will also be derived as a supportive analysis (see Table 2-2).

If more than one analysis visit occurs at a visit, only one will be selected for summary tables but all visits will be listed.

For categorical variables, the closest to the target study day is chosen (if two assessments have the same distance, than the earlier one will be chosen).

For continuous variables, the worst record is selected. It is noted that in the analyses performed, worst case is always well defined (e.g., for urine protein values "+" and "++", the worst case is defined as "++").

The analysis visit will be used for listing of visit and period. If a visit falls after the last visit window (i.e. after Day 435) it is not assigned an analysis visit and will be listed under the label "After last scheduled visit" (i.e. "After Week 60").

Table 2-1 Visit windows

Timepoint	Analysis visit	Target Study day	Visit window
	•		(study days)
	Baseline	1	-42 to 1
4	Week 1	8	2 to 11
5	Week 2	15	12 to 18
6	Week 3	22	19 to 25
7	Week 4	29	26 to 43
8	Week 8	57	44 to 71
9	Week 12	85	72 to 99
10	Week 16	113	100 to 127
11	Week 20	141	128 to 155
12	Week 24	169	156 to 183
13	Week 28	197	184 to 211
14	Week 32	225	212 to 239
15	Week 36	253	240 to 267
16	Week 40	281	268 to 295
17	Week 44	309	296 to 323
18	Week 48	337	324 to 351
19	Week 52	365	352 to 379
20	Week 56	393	380 to 407
21	Week 60	421	408 to 435

Table 2-2 Weekly period for co-administered prednisolone treatment

Timepoint	Week	Week definition
3	Week 0	Study day 1 to Study day 7
4	Week 1	Study day 8 to Study day 14
5	Week 2	Study day 15 to Study day 21
6	Week 3	Study day 22 to Study day 28
7	Week 4	Study day 29 to Study day 35
8	Week 5	Study day 36 to Study day 42
9	Week 6	Study day 43 to Study day 49
10	Week 7	Study day 50 to Study day 56
11	Week 8	Study day 57 to Study day 63
12	Week 9	Study day 64 to Study day 70
13	Week 10	Study day 71 to Study day 77
14	Week 11	Study day 78 to Study day 84
15	Week 12	Study day 85 to Study day 91
16	Week 13	Study day 92 to Study day 98
17	Week 14	Study day 99 to Study day 105

Timepoint	Week	Week definition
18	Week 15	Study day 106 to Study day 112
19	Week 16	Study day 113 to Study day 119
20	Week 17	Study day 120 to Study day 126
21	Week 18	Study day 127 to Study day 133
22	Week 19	Study day 134 to Study day 140
23	Week 20	Study day 141 to Study day 147
24	Week 21	Study day 148 to Study day 154
25	Week 22	Study day 155 to Study day 161
26	Week 23	Study day 162 to Study day 168
27	Week 24	Study day 169 to Study day 175
28	Week 25	Study day 176 to Study day 182
29	Week 26	Study day 183 to Study day 189
30	Week 27	Study day 190 to Study day 196
31	Week 28	Study day 197 to Study day 203
32	Week 29	Study day 204 to Study day 210
33	Week 30	Study day 211 to Study day 217
34	Week 31	Study day 218 to Study day 224
35	Week 32	Study day 225 to Study day 231
36	Week 33	Study day 232 to Study day 238
37	Week 34	Study day 239 to Study day 245
38	Week 35	Study day 246 to Study day 252
39	Week 36	Study day 253 to Study day 259
40	Week 37	Study day 260 to Study day 266
41	Week 38	Study day 267 to Study day 273
42	Week 39	Study day 274 to Study day 280
43	Week 40	Study day 281 to Study day 287
44	Week 41	Study day 288 to Study day 294
45	Week 42	Study day 295 to Study day 301
46	Week 43	Study day 302 to Study day 308
47	Week 44	Study day 309 to Study day 315
48	Week 45	Study day 316 to Study day 322
49	Week 46	Study day 323 to Study day 329
50	Week 47	Study day 330 to Study day 336
51	Week 48	Study day 337 to Study day 343
52	Week 49	Study day 344 to Study day 350
53	Week 50	Study day 351 to Study day 357
54	Week 51	Study day 358 to Study day 364
55	Week 52	Study day 365 to Study day 371
56	Week 53	Study day 372 to Study day 379
57	Week 54	Study day 380 to Study day 386
58	Week 55	Study day 387 to Study day 393
59	Week 56	Study day 394 to Study day 400

Page 17 of 53

Timepoint	Week	Week definition
60	Week 57	Study day 401 to Study day 407
61	Week 58	Study day 408 to Study day 414
62	Week 59	Study day 415 to Study day 421
63	Week 60	Study day 422 to Study day 429

Note: Co-administered treatment refers to prednisolone taken for GCA. There should be a 26-week prednisolone taper regimen however a patient may take additional prednisolone over the 52-week treatment period.

2.2 **Analysis sets**

The following analysis sets will be used for the patients of interest:

- The Randomized Analysis Set (RAS) consists of all randomized patients. Unless otherwise specified, mis-randomized patients will be excluded from the RAS. (Misrandomized patients are defined as cases where patients were mistakenly randomized by the investigator/qualified site staff either prematurely or inappropriately prior to confirmation of the patient's final randomization eligibility and double-blind treatment was not administered to the patient. If patients were re-screened and successfully randomized they will be included in the RAS according to the treatment assigned in the last randomization.)
- The Full Analysis Set (FAS) comprises all patients to whom study treatment has been assigned by randomization and who received at least one dose of randomized study treatment (secukinumab or placebo). According to the intent to treat principle, patients will be analyzed according to the treatment assigned to them at randomization.
- The Safety Set includes all patients who received at least one dose of study treatment (secukinumab or placebo). Patients will be analyzed according to the study treatment received, where treatment received is defined as the treatment the patient received on the first day of study treatment.

The number of patients within each of the analysis sets used in this study will be summarized by treatment group and overall (i.e. all patients).

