At every visit, each patient's disease activity and condition will be assessed in order to determine whether the patient can adhere to the defined prednisolone taper regimen (open-label fashion). If they cannot adhere to the taper regimen or are experiencing a flare (definition above), they must enter the "escape" arm and receive prednisolone at a dose determined by the physician based on clinical need and will continue to receive secukinumab 300 mg or placebo s.c. (still blinded).

Safety evaluation will be included in all visits including two safety follow-up visits performed 8 and 12 weeks after the last study drug administration at Week 48 (this will be at Week 56 and Week 60 for patients completing the study according to the protocol).

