2.4.3 Signs and symptoms of GCA

The number and percentage of patients who experienced flare due to GCA will be summarized by visit for each treatment group and overall (i.e. all patients). The summary table will also include the number and percentage of patients with each of the following individual signs and symptoms of GCA:

- Fever (Yes, No)
- Symptoms of polymyalgia rheumatica (PMR) (Yes, No)
- Localized headache, temporal artery or scalp tenderness (Yes, No)
- Acute or subacute vision loss due to arteritic anterior ischemic optic neuropathy(A-AION)
 (Yes, No)
- Transient blurry vision (generally monocular or at least affecting one eye at a time, but potentially affecting both eyes) (Yes, No)
- Jaw or mouth pain (Yes, No)
- New or worsened extremity claudication (Yes, No)
- Other features judged by both the clinician-investigator to be consistent with a GCA or PMR flare (Yes, No)

Note: More than 1 sign and symptom of GCA may be selected.

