2.7.2 Statistical hypothesis, model, and method of analysis

The proportion of patients in sustained remission until Week 52 (Yes, No) will be summarized descriptively for each treatment group. Note: Sustained remission at Week 52 refers to patients without flare until Week 52 and in adherence to the protocol prednisolone taper regimen. Flare is determined by the investigator and defined as the recurrence after remission of signs or symptoms of GCA and/or ESR \geq 30 mm/hr and/or CRP \geq 10 mg/L attributable to GCA. In addition, the reasons why a patient is determined to be a responder or non-responder to patients in sustained remission until Week 52 will be summarized.

The proportion of patients in remission (Yes, No) at each time point will be summarized descriptively for each treatment group. Note: Remission refers to the absence of flare. This summary table will only summarize remission information up to 4 weeks post last administration of study treatment.

The time to first GCA flare after remission (up to and including Week 52) will be summarized using Kaplan Meier curves. Descriptive statistics will also be provided for time to first GCA flare after remission in days (up to and including Week 52). This will also include information on follow-up. Follow-up is defined as:

• (Date of event or censoring – Baseline date) + 1 (regardless of censoring)

Total cumulative prednisolone dose from the first dose of co-administered prednisolone treatment to Weeks 26, Week 28, and 52 will be summarized over time by treatment group. Note: Prednisolone dose refers to prednisolone dose taken for GCA.

The number and percentage of patients on prednisolone dose \leq 5mg/day at Week 19, 28 and 52 will be summarized by treatment group. Note:

- Prednisolone dose refers to prednisolone dose taken for GCA.
- Prednisolone dose refers to the average co-administered prednisolone treatment in the week of interest.

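### The closest-to-target rule for categorical variables can drop an unscheduled flare from the by-visit flare and signs table (SAP 2.4.3), and SAP 2.7.3 should extend the escape rule to every visit of the remission table

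*SAP*

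**What the plan says.** SAP 2.1.1.12 assigns each visit to an analysis window by study day. Where a window holds more than one visit, "only one will be selected for summary tables but all visits will be listed". The choice depends on the type of variable:

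- Categorical: "For categorical variables, the closest to the target study day is chosen", with ties going to the earlier record.
- Continuous: "For continuous variables, the worst record is selected".

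Unscheduled visits take part, because SAP 2.1.1.5 opens its formula with "The study day for a baseline or post-baseline scheduled or unscheduled visit is defined as".

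Two planned tables use Yes/No disease status by visit:

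- SAP 2.4.3: "The number and percentage of patients who experienced flare due to GCA will be summarized by visit for each treatment group and overall". The same table counts eight individual GCA signs and symptoms. It has no any-record rule and no cumulative row.
- SAP 2.7.2: "The proportion of patients in remission (Yes, No) at each time point will be summarized descriptively for each treatment group". Remission there means only that flare is absent.

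Protocol 3.1 makes escape obligatory: if patients "are experiencing a flare (definition above), they must enter the" escape arm. Protocol 9.5.1 treats escaped patients as non-responders for remission from that point on. SAP 2.7.3 carries this rule over, but introduces it for the Week 12 remission rate.

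**The concern.** Flare is an event, and a Yes is the information sought. The closest-to-target rule favours the scheduled visit, which is normally near target. A patient who comes in between visits because of a flare is likely to be further away.

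After the flare the patient is on prednisolone at a physician-determined dose, so the next scheduled record may show no signs. The flare, and the type of flare (cranial, PMR, visual, fever), would then be missing from every row of the 2.4.3 table. That is the only planned table that breaks flares down by sign. With about 25 patients per arm, one dropped flare changes a visit row by 1/25 = 4 percentage points.

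The same section takes the worst record for continuous variables, so the event variable gets the less sensitive rule.

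**Working it through.** **Inputs.** Targets and windows come from SAP Table 2-1, and the selection and tie rules from SAP 2.1.1.12. Visit timing is an assumption: the protocol's visit schedule (Section 6) gives no day tolerance and asks only for visits as near the planned day as possible.

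**Windows reproduced.** Each upper limit is floor((target + next target)/2).

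- Week 12: starts at floor((57 + 85)/2) + 1 = 72 and ends at floor((85 + 113)/2) = 99.
- Week 28: starts at floor((169 + 197)/2) + 1 = 184 and ends at floor((197 + 225)/2) = 211.

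Every boundary from Week 1/2 to Week 56/60 matches. From Week 8 on, each window has 28 days, from target −13 to target +14.

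**Worked case.** Scheduled Day 197 shows no flare; unscheduled Day 206 shows a flare. Both lie in 184–211. The distances are 0 and 9, so Day 197 is kept and Week 28 reads no flare. The next target is Day 225, 225 − 206 = 19 days after the flare. If the signs have gone by then, no row shows it.

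**Share of pairs that lose the flare.** Take one scheduled no-flare record, uniform on target ±d, and one unscheduled flare record, uniform on the other 27 days of the window.

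- Scheduled record a days after target: 2a − 1 days are strictly closer, and the tie at −a goes to the flare because it is earlier. The flare is kept on 2a of 27 days.
- Scheduled record a days before target: the tie goes to the scheduled record. The flare is kept on 2a − 1 of 27 days.
- Summing 4a − 1 over a = 1 to d gives d(2d + 1) of 27(2d + 1) pairs. The flare is kept in d/27 of pairs and dropped in 1 − d/27.

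| Scheduled visit within | Flare record dropped |
|---|---|
| on target | 27/27 = 100% |
| ±1 day | 26/27 = 96% |
| ±3 days | 24/27 = 89% |
| ±5 days | 22/27 = 81% |
| ±7 days | 20/27 = 74% |
| ±10 days | 17/27 = 63% |

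A full enumeration of day pairs gives the same values. In the shorter Week 4 window (Days 26–43, target 29), with the scheduled visit kept inside the window, it gives 100%, 94%, 82%, 76%, 71% and 62%.

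**Remission table with the escape rule applied at every visit.** In the Week 12 window with the scheduled visit on Day 85:

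- A flare on Day 75 leads to escape before Day 85. Week 12 is non-response whichever record is kept.
- A flare on Day 95 can leave Week 12 as remission, but the patient is a non-responder from Week 16 on.

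The one-visit delay needs the scheduled record to be kept and to precede the flare. Counting those pairs gives (14 + 28d − d²) / (27(2d + 1)): 14/27 = 52% on target, 89/189 = 47% at ±3 days and 161/405 = 40% at ±7 days. None is lost permanently.

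**Remission table without the escape rule.** If windowed flare status alone were used after Week 12, the Day 197/Day 206 patient could read as in remission at both Week 28 and Week 32.

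**The case against.** **A by-visit table reports status at a visit.** Closest-to-target is a reasonable choice for that purpose, and an any-Yes rule measures incidence over an interval, which depends on how often a patient is seen. This has some force, and it is why an ever-flared row is an acceptable alternative. But SAP 2.4.3 counts patients who experienced a flare, which reads as an event count.

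**The premise is thinly documented.** Protocol 6.3.1.1 ties the GCA assessment to scheduled visits, and the readable part of Table 6-1 has no unscheduled column. The SAP gives unscheduled visits a study day but does not say that the GCA assessment is done there. This stands as a limit on frequency. It does not change what the rule does when such a record exists.

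**The percentages are conditional.** A reader might take 63% to 100% as the share of all flares lost. The documents do not support that. The figures apply only to windows holding both an unscheduled flare record and a scheduled no-flare record. If the scheduled visit is missed, or still shows the flare, nothing is lost.

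**The remission results are protected.** A reader might infer that the flare also vanishes from these. The documents point the other way: flare obliges escape, protocol 9.5.1 carries non-response forward, the SAP says that it follows protocol Section 9, and SAP Section 4 does not withdraw the rule. What remains is a gap in wording, because SAP 2.7.3 ties the rule to Week 12, although its reference to what follows escape can be read more broadly.

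**Arm comparison.** A reader might infer that every measure of the arm difference shrinks. If the same share q is lost in both arms, the absolute difference is multiplied by 1 − q and the ratio is unchanged. The plan does not settle whether the shares would be equal.

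**Conclusion.** The point holds for the by-visit flare and signs table. As written, SAP 2.1.1.12 drops an unscheduled flare whenever a scheduled no-flare record in the same window is closer to target, and that flare may then be absent from the whole table. The loss is 63% to 100% of such pairs in the 28-day windows. This rests on evenly spread unscheduled visits and scheduled visits 0 to ±10 days from target; the number of such pairs is unknown.

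For the by-visit remission table the effect is a delay of at most one visit under the protocol 9.5.1 rule. It would be larger only if SAP 2.7.3 were applied literally to Week 12 alone.

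Nothing that drives a decision is touched. Sustained remission to Week 28 and to Week 52 is cumulative and counts escape as non-response, the GO criteria in SAP 2.5.2 use only the Week 28 endpoint, time to first flare runs on dates, and all visits stay in the listings. Severity is minor: descriptive output only.

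**What to change.** 1. In SAP 2.1.1.12, add an exception for flare and the individual GCA signs and symptoms: a window counts as Yes if any record in it is Yes. Alternatively, leave the rule as it is and add a cumulative ever-flared row, with signs, to the SAP 2.4.3 table.
2. In SAP 2.7.3, state that the protocol 9.5.1 rule (non-responder from escape onwards) applies at every time point of the remission table.
3. Keep closest-to-target for all other categorical variables.

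The cost is a sentence in each section and a small programming change. No new data are needed and the primary analysis is unchanged. The downside of the any-Yes rule is that windows with extra visits have more chances to show a flare. That is acceptable for an event variable, and a table footnote can say so.

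### Selecting the worst record per visit window for continuous variables, against a last-value baseline, shifts by-visit change scores toward worsening wherever a window holds more than one record

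*SAP*

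**What the plan says.** SAP 2.1.1.12 assigns each record to an analysis visit by its study day. If several fall in one window, "only one will be selected for summary tables but all visits will be listed". The choice then depends on the type of variable. "For categorical variables, the closest to the target study day is chosen", with the earlier record taken in a tie. "For continuous variables, the worst record is selected". The SAP adds that "worst case is always well defined"; its only example is an ordinal urine test, introduced by "for urine protein values".

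Unscheduled records enter the windows because SAP 2.1.1.5 gives them a study day: "The study day for a baseline or post-baseline scheduled or unscheduled visit is defined as".

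Baseline follows a different rule. SAP 2.1.1.7 says that "The baseline value for efficacy and safety variables is the last available, non-missing, (scheduled or unscheduled) value" before the first dose, so it is not chosen by its size.

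SAP 2.7.2, 2.8.3, 2.8.4.1 and 2.10 then summarise change from baseline by visit and arm for PhGA, CRP, ESR, laboratory tests, vital signs, PGA, FACIT-Fatigue, SF-36 and EQ-5D. None of these sections gives another selection rule, and no analysis restricted to scheduled records is planned.

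**The concern.** Baseline is one unselected measurement, but the post-baseline value is an extreme whenever there is a choice. Measurement noise alone then pushes the change score toward worsening (up for CRP, ESR, PhGA and PGA; down for FACIT-Fatigue, SF-36 and EQ-5D), never toward improvement.

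If one arm has more windows with extra records, its mean moves further and a difference appears that treatment did not cause. The SAP introduction says that the study report is meant to support a phase III programme, so readers will look at these secondary profiles.

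A smaller point concerns safety data: for measures that can be abnormal in both directions, the SAP does not say which record is the worst.

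**Working it through.** The SAP states no figure for this rule, so there is none to reproduce.

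**1. Where a second record can come from.** The 18 post-baseline windows in SAP Table 2-1 are contiguous. They are 10, 7, 7 and 18 days wide up to Week 4 and 28 days wide from Week 8. Each holds exactly one target day. A second record must therefore come from an unscheduled, repeat, displaced or early-termination visit. The protocol documents three routes:
- Repeat laboratory evaluation is mandatory after clinically relevant deviations (6.4.5).
- Patients in escape keep attending scheduled visits (3.1), so a record made at a flare can share a window with a scheduled one.
- Patients who leave the study return for the Week 52 assessments (5.6.2 and 6), which include PhGA and the patient-reported outcomes (Table 6-1).

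**2. Shift in a window with two records, no true change.** For two normal records with common mean and SD and correlation r, the worse one lies on average SD × √((1−r)/π) beyond the mean:
- r = 0: √(1/π) = 0.56 SD
- r = 0.5: √(0.5/π) = 0.40 SD
- r = 0.8: √(0.2/π) = 0.25 SD

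Three uncorrelated records give 0.85 SD; one record gives 0. The documents do not give r.

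**3. Difference between arms, noise only.** If a share f of an arm's windows has two records, the arm mean shifts by f times the value in step 2. Assume 20% on placebo and 5% on secukinumab (neither is in the documents), a gap of 0.15:
- 0.15 × 0.25 = 0.04 SD
- 0.15 × 0.40 = 0.06 SD
- 0.15 × 0.56 = 0.08 SD

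At equal rates the difference is 0, although both arms still shift (at 10% each and r = 0, by 0.10 × 0.56 = 0.06 SD).

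**4. Extra record with a real flare shift.** Let the scheduled record be N(0,1) and the extra one N(d,1), in units of within-patient SD, which equals SD × √(1−r). The expected gain from taking the worse one is d·Φ(d/√2) + √2·φ(d/√2), which is 0.56, 1.20 and 2.05 for d = 0, 1 and 2. Multiplying by the assumed gap in rates:

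| Extra records, secukinumab vs placebo (assumed) | d = 0 | d = 1 | d = 2 |
|---|---|---|---|
| 10% vs 10% | 0 | 0 | 0 |
| 5% vs 15% | 0.06 | 0.12 | 0.21 |
| 5% vs 20% | 0.08 | 0.18 | 0.31 |
| 10% vs 30% | 0.11 | 0.24 | 0.41 |

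Simulation with 2,000,000 patients per setting, at rates of 10% and 30%, agreed with the formula to within 0.002.

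**5. Scale.** With 25 per arm, the standard error of a difference in mean change is √(2/25) = 0.28 SD of the change score. At r = 0.5 the variance of a change is 2(1−0.5)SD² = SD², so the noise-only artefact is 0.06/0.28 = 0.21 of a standard error. For 5% vs 20% and d = 2 it is 0.31 × √0.5 = 0.22 SD, or 0.22/0.28, about 0.8 of a standard error.

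**6. Two-sided measures.** Protocol Table 13-1 gives one-sided notable limits for some tests, including a low limit for white cells. It gives none for potassium, glucose, blood pressure or weight. SAP 2.8.3 classifies laboratory shifts as low, normal, high, or low and high, which already recognises that both directions matter.

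**The case against.** The strongest reply is that the mechanism for a difference between arms is not documented. Neither document says that unscheduled visits cluster around flares, and the published Table 6-1 shows no unscheduled-visit column. The planned sustained-remission rates of 56% and 18% (SAP 2.5.2) suggest unequal flares, not unequal numbers of extra records. This stands. A reader might infer that the rule will exaggerate the benefit of secukinumab; the documents support only that it could.

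Second, exposure is uneven. PhGA and the patient-reported outcomes are tied to the visits in Table 6-1, so they are duplicated only by off-schedule collection, such as an early-termination visit. Where a laboratory repeat merely follows an abnormal scheduled value, the worst record is usually that scheduled value, and little is added. Both points stand and limit the scope.

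Third, the consequences are modest. The affected endpoints are summarised descriptively, there are no key secondary objectives (SAP 2.6), and the primary endpoint and GO criteria rest on a binary outcome. This stands too.

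Fourth, it would go too far to call the worst case undefined for every two-sided test. White cells have a stated low limit, laboratory shift tables already handle high and low, and the master analysis plans that the SAP cites are not available here. What remains is that this SAP does not support its statement for the measures in step 6.

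Finally, a worst value can be informative, because a later record may reflect escape prednisolone. That argues for showing worst values separately, not for placing them in a change score against an unselected baseline.

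**Conclusion.** The asymmetry is real and follows from the SAP's own text. In a window with two records, change from baseline shifts toward worsening by 0.25 to 0.56 SD for r between 0.8 and 0, assuming normal errors; in a window with one record there is no shift. CRP and ESR are the most exposed.

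A false difference between arms is conditional. It needs extra records to be more frequent in one arm, for which the documents give no rates. At an assumed 20% vs 5% it is about 0.04 to 0.08 SD from noise, and larger if the extra records are true flare values. If placebo has the excess, the artefact favours secukinumab.

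Only descriptive secondary and safety summaries are affected. The change is worth making because it is cheap and the SAP already applies an outcome-neutral rule to categorical data.

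**What to change.** In SAP 2.1.1.12, replace the sentence on continuous variables. For by-visit summaries, use the record from the scheduled visit that belongs to the window. If there is none, use the record closest to the target day, taking the earlier in a tie. Early-termination assessments should count as off schedule for this purpose. Preferring the scheduled record matters: choosing by day alone can still pick a flare record that lies nearer the target, leaving a bias of f × q × d, where q is the chance that this happens. In the simulation, using the scheduled record brought the bias to zero (−0.002 to 0.002).

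Keep worst-value selection for the existing low/high laboratory shift tables and for listings. State the adverse direction wherever a single worst value is still used, and state that SAP 2.1.1.7, not the window rule, governs the Baseline window in Table 2-1.

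The cost is one SAP sentence with these clarifications and one programming rule. By-visit tables would no longer show off-schedule worst values. These remain in the listings and, for laboratory tests, in the shift tables; vital signs have listings only.
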